#### LIST OF ABBREVIATIONS

Term	Definition
AE	Adverse Event
CFR	Code of Federal Regulations
eCRF	Electronic Case Report Form
CRO	Contract Research Organization
DCF	Data Clarification Forms
EC	Ethics Committee
ED	Early Discontinuation Visit
EDC	Electronic Data Capture
EOT	End of Treatment Visit
FDA	Food and Drug Administration
GCP	Good Clinical Practice
HEENT	Head, Eyes, Ears, Nose and Throat
HIPAA	Health Insurance Portability and Accountability Act
ICF	Informed Consent Form
ICH	International Council for Harmonization
ID	Identification
IEC	Institutional Ethics Committee
IOP	Intraocular Pressure
IRB	Institutional Review Board
IU	International Unit
IUD	Intrauterine Device
IWRS	Interactive Web Response System
LOCF	Last Observation Carried Forward
mITT	Modified Intent to Treat
NA	Not Applicable
NSAID	Non-Steroidal Anti-Inflammatory Drug
SAE	Serious Adverse Event
UPT	Urine Pregnancy Test
US	United States
USV	Unscheduled Visit
WOCBP	Women of child bearing potential

#### Protocol Synopsis

Sponsor:	Name of Medical Products:	Active Ingredient(s):
Actavis LLC	Nepafenac and Ilevro TM (Nepafenac ophthalmic suspension)	Nepafenac

#### Study Title, Design and Methodology:

A randomized, multicenter, double masked, placebo controlled, parallel group, bioequivalence study to evaluate the clinical equivalence and safety of Nepafenac 0.3% ophthalmic suspension

Actavis LLC) with IlevroTM (Nepafenac ophthalmic

suspension), 0.3% of Alcon Laboratories, Inc. for the treatment of pain and inflammation associated with cataract surgery.

#### Number of Subjects to be Enrolled and Randomized (Planned):

Approximately 450 subjects , who have a cataract and are planning to undergo cataract surgery will be enrolled and randomized .

#### **Study Sites:**

This multicenter study will be conducted at approximately 17 study sites in the U.S.

#### Indication:

Pain and inflammation associated with cataract surgery

#### **Study Phase:**

Bioequivalence study with clinical endpoint

#### **Study Objectives**:

- To demonstrate the clinical equivalence of Nepafenac 0.3% ophthalmic suspension Actavis LLC.) with IlevroTM (Nepafenac ophthalmic suspension), 0.3% of Alcon Laboratories, Inc. for the treatment of pain and inflammation associated with cataract surgery.
- To demonstrate the superiority of the efficacy of the test and reference products over the placebo control in the treatment of pain and inflammation associated with cataract surgery.

#### **Study Duration:**

Total study duration will be of 16 days i.e. the treatment duration. A Screening period of up to 21 days is acceptable.

#### **Diagnosis/Target Population and Key Inclusion Criteria:**

Study will be conducted on subjects who have a clinical diagnosis of cataract and are planning to undergo cataract surgery.

The study is designed to be only monocular (only one eye per subject).

Other inclusion and exclusion criteria are mentioned in sections 4.2 and 4.3 of the protocol.

Sponsor:	Name of Medical Products:	Active Ingredient(s):
Actavis LLC	Nepafenac and Ilevro ™ (Nepafenac ophthalmic	Nepafenac
	suspension)	
Investigational P	oducts:	
TEST PRODUC	Т:	
Name of the prod	uct: Nepafenac	
1	osage form: Ophthalmic suspension	
Strength: 0.3%		
Manufactured by:	Actavis LLC.	
REFERENCE P	RODUCT:	
Name of the proc	uct: Ilevro TM (Contains Nepafenac)	
Pharmaceutical d	osage form: Ophthalmic suspension	
Strength: 0.3%		
Manufactured by:	Alcon Laboratories, Inc	
-		
PLACEBO:		
Name of the prod	uct: Sterile ophthalmic suspension	
Pharmaceutical de	osage form: Ophthalmic suspension	
Strength: NA		
U U		
Manufactured by:	Actavis LLC.	

A drop of the study drug suspension should be instilled into the affected eye one-time daily, beginning a day prior to the planned cataract surgery, on the day of the cataract surgery and for 14 days thereafter. The study drug should be instilled once daily. On the day of cataract surgery (Day 0) a drop should be added 30-120 minutes prior to the surgery and once following cataract surgery prior to the subject leaving the surgery center.

Note: As the study drug will be administered twice on the day of cataract surgery (Day 0) once prior to cataract surgery and once following cataract surgery prior to the subject leaving the surgery center. The dose and mode of treatment chosen in this study is the dosage approved by US FDA for the treatment of pain and inflammation associated with cataract surgery.

At least 5 minutes between all ophthalmic drop administrations should be maintained throughout the study.

Clinical Evaluations will be performed at:

- Visit 1: Day -21 to Day -1 (Screening/Baseline/Randomization Visit) Pre-Operative Call: Day -1
- Visit 2: Day 0 (The Day of Cataract Surgery)
- Visit 3: Day 1 (One Day After Cataract Surgery)
- Visit 4: Day 7± 2 Days (Follow-up Visit)
- Visit 5: Day 14 ± 2 Days (End of Study Visit/ Early Discontinuation)

Sponsor:	Name of Medical Products:	Active Ingredient(s):
Actavis LLC	Nepafenac and Ilevro ™ (Nepafenac ophthalmic	Nepafenac
	suspension)	

# **Clinical Endpoints:**

Evaluation of Efficacy:

Proportion of subjects with cure at Day 14 defined as a score of 0 for aqueous cells, a score of 0 for aqueous flare and a score of no more than 3 for pain.

Evaluation of Safety:

- The incidence of treatment emergent adverse events.
- Ocular parameters (visual acuity, intraocular pressure measurement, slit lamp evaluation and dilated fundus examination)

#### Table No. 1:

Grade	Aqueous Cells: Determined using a narrow slit beam (0.5 mm width at least
	8mm length) at maximum luminance. Pigment and red blood cells are to be
0	None
1	1 to 5 cells
2	6 to 15 cells
3	16 to 30 cells
4	Greater than 30 cells
Grade	Aqueous Flare: Determined using a narrow slit beam (0.5 mm width at least 8mm length) at maximum luminance.
0	No visible flare when compared with the normal eye.
1	Mild-Flare visible against dark pupillary background but not visible against iris
	background.
2	Moderate-Flare is visible with the slit-lamp beam aimed onto the iris surface as
3	well as the dark pupillary background.
3	Severe-Very dense flare. May also present as a "hazy" appearance of anterior
	segment structures when viewed with low power magnification of the slit-lamp. Present as pronounced Tyndall effect.
Grade	Ocular Pain: A positive sensation of the eye, including foreign body sensation,
	stabbing, throbbing or aching.
0	None- absence of positive sensation
1	Patient reports presence of mild sensation or discomfort typical of post-operative
	ocular surgery, e.g., diffuse or focal foreign body sensation, mild transient
	burning or stinging.
2	Mild- mild, tolerable aching of the eye.
3	Moderate- moderate or more prolonged aching sufficient to require the use of
	over-the-counter analgesics (e.g. acetaminophen).
4	Moderately Severe- More prolonged aching requiring the use of any over-the-
	counter analgesics other than acetaminophen.
5	Severe- Patient reports intense ocular, periocular, or radiating pain (e.g., constant
	or nearly constant sharp stabbing pain, throbbing or aching, etc.) requiring
	prescription analgesics.

[figure not shown]
## **STATISTICAL METHODS:**

#### SAMPLE SIZE ESTIMATION:

To establish bioequivalence for the primary endpoint (proportion of subjects with "cure" at the Day 14), the 90% confidence interval of the test - reference difference between products must be contained within [-0.20, +0.20] for dichotomous variables (cure versus failure), using the PP population.

#### TEST OF EQUIVALENCE:

• The PP population includes all randomized subjects who meet all inclusion and exclusion criteria,

• The safety population includes all randomized subjects who receive study drug.

Subjects who discontinue because of lack of treatment effect after completing two days of treatment should be analyzed in the mITT and PP populations as a treatment failure. Subjects discontinued for other reasons, including drug-related adverse events, should be excluded from the PP population, but included in the mITT population using Last Observation Carried Forward (LOCF).

The recommended primary endpoint is the proportion of subjects with cure at Visit 5 (end of the study on day  $14 \pm 2$  days) defined as a score of 0 for aqueous cells, a score of 0 for aqueous flare and a score of no more than 3 for pain.

#### SAFETY PARAMETERS:

Incidence of all adverse events reported during the study will be summarized using the current version of MedDRA dictionary by treatment group, body system, severity and relationship to study drug. No inferential statistical analyses are planned.

#### **1.0 INTRODUCTION AND BACKGROUND**

#### **Rationale for the Study**

This study is designed to determine clinical equivalence of an ophthalmic suspension in order to facilitate the registration of a generic version of Nepafenac 0.3% suspension. The reference listed drug for this suspension is  $Ilevro^{TM}$  (Nepafenac Ophthalmic Suspension 0.3%). This study will be conducted in male and female subjects with cataract.

#### **Overview of Study Indication**

Some degree of post-operative ocular inflammation remains a predictable consequence of a cataract surgery and intraocular lens implantation. Ocular inflammation is characterized by redness, swelling, and/or pain associated with irritation or trauma to the eye. Surgical trauma causes a trigger of the arachidonic acid cascade which in turn generates prostaglandins by activation of Cyclo-oxygenase-1 and Cyclo-oxygenase-2.

Clinical symptoms of prostaglandin production include hyperemia, miosis, impaired vision, pain and diminished visual acuity secondary to cystoid macular edema (CME).

Clinically, iritis is the hallmark of intra-ocular inflammation, characterized by perilimbal injection and anterior chamber cell and flare. If not treated appropriately, this inflammation can result in significant discomfort for subjects and impede the recovery of the vision. Cystoid macular edema is another vision reducing complication that can occur as a consequence of the post-operative ocular inflammatory response.

[figure not shown]
Topical NSAIDs reduce inflammation by inhibiting prostaglandin synthesis and have been shown to be clinically effective in controlling inflammation after cataract surgery. Several clinical studies have shown that NSAIDs are as effective as steroids in the treatment of post-operative pain and inflammation.

#### **Current Treatment for Study Indication**

Topical NSAIDs which are used commonly for ocular pain and inflammation are Diclofenac, Ketorolac, Bromfenac, and Nepafenac. Topical steroids used commonly for the same are Loteprednol, Triamcinolone, Rimexolone, Medrysone, Prednisolone, and Dexamethasone.

#### **Reference Product Information (ILEVROTM)**

ILEVROTM (nepafenac ophthalmic suspension), 0.3% is a sterile, topical, nonsteroidal antiinflammatory (NSAID) prodrug for ophthalmic use. Each mL of ILEVROTM (nepafenac ophthalmic suspension), 0.3% contains 3 mg of nepafenac. Nepafenac is designated chemically as 2-amino-3-benzoylbenzeneacetamide with an empirical formula of C15H14N2O2. The structural formula of nepafenac is:

Nepafenac is a yellow crystalline powder. The molecular weight of nepafenac is 254.28. ILEVROTM (nepafenac ophthalmic suspension), 0.3% is supplied as a sterile, aqueous suspension with a pH approximately of 6.8. The osmolality of ILEVROTM (nepafenac ophthalmic suspension), 0.3% is approximately 300 mOsm/kg.

Each mL of ILEVROTM (nepafenac ophthalmic suspension), 0.3%, contains: Active: nepafenac 0.3% Inactives: boric acid, propylene glycol, carbomer 974P, sodium chloride, guar gum, carboxymethylcellulose sodium, edetate disodium, benzalkonium chloride 0.005% (preservative), sodium hydroxide and/or hydrochloric acid to adjust pH and purified water, USP.

#### Mechanism of Action/Pharmacodynamics

After topical ocular dosing, nepafenac penetrates the cornea and is converted by ocular tissue hydrolases to amfenac, a nonsteroidal anti-inflammatory drug. Nepafenac and amfenac are thought to inhibit the action of prostaglandin H synthase (cyclooxygenase), an enzyme required for prostaglandin production.

#### **Pharmacokinetics**

Following bilateral topical ocular once-daily dosing of ILEVROTM (nepafenac ophthalmic suspension), 0.3%, the concentrations of nepafenac and amfenac peaked at a median time of 0.5 hour and 0.75 hour, respectively on both Day 1 and Day 4. The mean steady-state Cmax for nepafenac and for amfenac were  $0.847 \pm 0.269$  ng/mL and  $1.13 \pm 0.491$  ng/mL, respectively.

Nepafenac at concentrations up to 3000 ng/mL and amfenac at concentrations up to 1000 ng/mL did not inhibit the in vitro metabolism of 6 specific marker substrates of cytochrome P450 (CYP) isozymes (CYP1A2, CYP2C9, CYP2C19, CYP2D6, CYP2E1, and CYP3A4). Therefore, drug-drug interactions involving CYP mediated metabolism of concomitantly administered drugs are unlikely.

#### 2.0 OBJECTIVES

- To demonstrate the clinical equivalence of Nepafenac 0.3% ophthalmic suspension (Actavis LLC) with IlevroTM (Nepafenac ophthalmic suspension), 0.3% of Alcon Laboratories, Inc. Fort Worth, Texas 76134 USA, for the treatment of pain and inflammation associated with cataract surgery.
- To demonstrate the superiority of the efficacy of the test and reference products over the placebo control in the treatment of pain and inflammation associated with cataract surgery.

### 3.0 STUDY OVERVIEW

Approximately 450 subjects **and are planning**, subjects who have a cataract and are planning to undergo cataract surgery will be enrolled and randomized in this investigational study.

One drop of the suspension should be instilled into the affected eye one-time daily, beginning a day prior to the planned cataract surgery, on the day of the cataract surgery, and for 14 days thereafter. On the day of cataract surgery (day 0) a drop should be added 30-120 minutes prior to the surgery and an additional drop will be administered following cataract surgery prior to the subject leaving the surgery center. The study is designed to be only monocular (only one eye per subject).

The dose and mode of treatment chosen in this study is the dosage approved by US FDA for the treatment of pain and inflammation associated with cataract surgery.

The study subjects will undergo clinical evaluations throughout the study in order to assess efficacy and safety. Study subject primary endpoint evaluation will be assessed on Visit 1 (-21 to -1 Days prior to cataract surgery), Visit 3 (Day after the cataract surgery), Visit 4 (Follow up Visit Day  $7 \pm 2$  days) and Visit 5 (End of study Day  $14 \pm 2$  days).

If the Investigator determines that the study subject's condition has worsened to the degree that it is unsafe for continuation in the study, the study subject may be discontinued and will be evaluated as a treatment failure.

#### 4.0 STUDY POPULATION

#### 4.1 Number of Study Subjects

This multicenter study will be comprised of subjects who have cataract and are planning to undergo cataract surgery.

Approximately 450 subjects aged 18 years and above, male or female, of any race, who meet all the inclusion and none of the exclusion criteria, will be enrolled into the study.

#### 4.2 Inclusion Criteria

1. Males or non-pregnant, non-lactating females, 18 years of age or older who have a cataract and are expected to undergo cataract extraction.

2. No aqueous cells, no visible aqueous flare and no significant ocular pain in the selected eye noted during the Screening visit by slit-lamp examination.

No aqueous cells	Grade 0
No visible aqueous flare	Grade 0
No significant ocular pain	Grade 0 or 1
For details See Table 1 on page 13	

- 3. Study subjects must have provided IRB approved written informed consent using the latest version of the IRB informed consent form. In addition, study subjects must sign a HIPAA authorization, if applicable.
- 4. Study subjects should be literate and willing to complete the subject diary regularly as directed.
- 5. Study subjects must be in good health and free from any clinically significant disease apart from indication under study.
- 6. Females of child bearing potential (WOCBP\*) must not be pregnant or lactating at baseline visit (as documented by a negative urine pregnancy test).
  \*All female subjects will be considered to be of childbearing potential unless they are postmenopausal. Female subjects of childbearing potential (WOCBP) are defined as sexually mature women without prior hysterectomy, or who have had any evidence of menses in the past 12 months. However, women who have been amenorrheic for the past 12 or more months are still considered to be of childbearing potential, if the amenorrhea is possibly due to other causes, including prior chemotherapy, antiestrogens, or ovarian suppression. Postmenopausal women (defined as women who have been amenorrheic for at least 12 consecutive months, in the appropriate age group, without other known or suspected primary cause) or women who have been sterilized surgically or who are otherwise proven sterile (i.e., total hysterectomy, or bilateral oophorectomy with surgery at least 4 weeks prior to randomization) are not considered WOCBP. Subjects who have undergone tubal ligation are NOT considered as surgically sterile.
- 7. Female subjects of childbearing potential must be willing to use an acceptable form of birth control from the day of the first dose administration to 30 days after the last administration of IP. For the purpose of this study the following are considered acceptable methods of birth control: oral or injectable contraceptives, contraceptive patches, Depo-Provera® (Medroxyprogesterone acetate-stabilized for at least 3 months); vaginal contraceptive; contraceptive implant; double barrier methods ( e.g. condom and spermicide); Nuvaring vaginal hormonal birth control, IUD, or abstinence with a second method of birth control should the subject become sexually active. A

sterile sexual partner is NOT considered an adequate form of birth control.

- 8. All male subjects must agree to use accepted methods of birth control with their partners, from the day of the first dose administration (to 30 days after the last administration of study drug). Please see acceptable forms for "Female" birth control above. Abstinence is an acceptable method of birth control for males.
- 9. Study subjects must be willing and able to understand and comply with the requirements of the protocol, including attendance at the required scheduled study visits.
- 10. Study subjects must be willing to refrain from using any other treatments other than the investigational product.

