#### 43 Exclusion Criteria

- 1. Females who are pregnant, breast feeding, or planning a pregnancy during the course of the study and for 30 days after last study dose.
- 2. Females of childbearing potential who do not agree to utilize an adequate form of contraception.
- 3. Current or past history of severe hepatic or renal impairment, uncontrolled diabetes mellitus, rheumatoid arthritis or bleeding tendencies.
- 4. Current or history within two months prior to baseline of clinically significant ocular disease, e.g., corneal denervation, corneal epithelial defects, severe dry eye syndrome, ocular trauma to the operative eye, corneal edema, proliferative diabetic retinopathy in the operative eye or ocular infection.
- 5. In the operative eye, history of chronic or recurrent inflammatory disease, e.g., iritis, scleritis, uveitis, iridocyclitis or rubeosis iritis, lens pseudoexfoliation syndrome with glaucoma or zonular compromise.
- 6. Congenital ocular anomaly, e.g., aniridia or congenital cataract in the operative eye.
- 7. Iris atrophy in the operative eye in the operative eye.
- 8. Current corneal abnormalities that would prevent accurate IOP readings with the Goldmann applanation tonometer in the operative eye.
- 9. Nonfunctional nonoperative eye (visual acuity of 20/200 or worse Snellen).
- 10. Known hypersensitivity to any component of nepafenac therapy or to other nonsteroidal anti-inflammatory drug (NSAID).
- 11. Use within one week prior to baseline in either eye of: Topical, ophthalmic, e.g. cyclosporine (Restasis®), or systemic NSAID.

- 12. Use within one month prior to baseline in either eye of: 1) systemic corticosteroid, 2) high-dose salicylate therapy, or 3) topical ophthalmic prostaglandin analogs, e.g., bimatoprost, latanoprost, or travoprost.
- 13. Use of systemic analgesic medications, e.g. narcotics, tramadol, Neurontin® within 48 hours of baseline. Exceptions are salicylate therapy 81mg or less per day, and acetaminophen not within 8 hours of any visit from Visit 1 until V5.
- 14. Use within six months prior to baseline of intravitreal or subtenon injection of ophthalmic corticosteroid in either eye.
- 15. Underwent within six months prior to baseline any complicated intraocular surgery or repeat ocular surgeries (e.g., cataract surgery) in the operative eye.
- 16. Underwent within twelve months prior to baseline: refractive surgery, filtering surgery or laser surgery for IOP reduction in the operative eye.

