#### 8.0 STUDY VISITS

#### 8.1 Visit 1: Screening/Baseline/Randomization Visit (Day-21 to day -1):

The following procedures will be performed at Visit 1:

1. Informed consent will be obtained from all participants who have confirmation on the

diagnosis of cataract and are planning to undergo cataract surgery. The latest version of IRB approved Informed Consent Form will be used for consenting process. The study subject will be allowed as much time as needed to read and understand the information presented in the informed consent form. Appropriate study personnel will be available to answer any questions the study subject might have regarding the study or study-related procedures. If the study subject chooses to participate in the study, he or she will be asked to sign and date the consent form and will be provided with a copy of the signed and dated consent form for his or her reference.

- 2. A complete medical history will be recorded. Information regarding the subject's current and past medical conditions will be captured including surgical procedures.
- 3. Review of prior medications which have been stopped/ongoing within 30 days prior to screening.
- 4. Demographics (Height, Weight, Age, Sex, Race/Ethnicity).
- 5. Physical Examination and Vital signs. At a minimum, the physical examination will include the following: assessment of general appearance, skin, HEENT, heart, lungs, musculoskeletal system, lymph nodes, neurological systems, gastrointestinal system, genitourinary system and extremities.
- 6. Assessment of ocular pain.
- 7. The study subject will be evaluated for iris color and complete slit lamp examination including a grading of the aqueous cells and aqueous flare.
- 8. Visual Acuity.
- 9. Intraocular pressure.
- 10. Fundus Examination.
- 11. A urine pregnancy test will be conducted for all females of childbearing potential.
- 12. The laboratory evaluation for routine hematology, biochemistry and urine analysis tests.
- 13. Assessment of any concomitant medications.
- 14. When the study subject has completed all screening procedures, the available data will be verified with the inclusion and exclusion criteria. Subject will be excluded from the study if any eligibility criterion is not satisfactory by the available information.
- 15. If eligibility criteria are satisfactory with the available information, the cataract surgery will be scheduled.
- 16. Randomize the patient in the study. CONFIDENTIAL

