#### 8.2 Visit 2: The Day of Cataract Surgery (Day 0):

- 1. Verification of study drug administration one day prior to surgery as required. Failure to comply with Day -1 study drug administration will result in the subject either proceeding with cataract surgery as scheduled but being withdrawn from the study, rescheduling of cataract surgery within 7 days of Screening/Baseline/Randomization Visit and proceeding on study, or cancellation of surgery and withdrawal from study.
- 2. Vital signs
- 3. Urine Pregnancy Test (for all females of childbearing potential)
- 4. Assessment of any concomitant medication
- 5. Assessment of Adverse Events
- 6. Administration of study drug to the operative eye should be administered 30-120 minutes prior to cataract surgery. (Administration of study drug should only be performed by the patient, caregiver, independent study drug administrator or unmasked personnel that are not assigned any other study duties). No masked members of staff should be involved in drug administration.

An additional drop of study drug should be administered post cataract surgery prior to the subject leaving the surgery center. (Administration of drug should only be performed by the patient, caregiver, independent study drug administrator or unmasked site personnel that are not assigned any other study duties). No masked members of staff should be involved in drug administration. The study is designed to be only monocular (only one eye per subject).

 Investigator should use the standard surgical methods, regimen of pre-operative and post-operative medication with the exception of NSAIDs and/or steroidal usage. CONFIDENTIAL Page 25 of 63

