## **13.5 Recording and Reporting of Adverse Events**

In this study, safety will be assessed by qualified study personnel by evaluating reported adverse events, clinical laboratory test results, vital signs measurements, physical examination findings (including body weight and height measurements), and use of concomitant medication.

For adverse event recording, the study period is defined for each subject as that time period from signature of the informed consent form through the end of the study (including the follow up period).

All adverse events that occur during the defined study period must be recorded on the source documentation, regardless of the severity of the event or judged relationship to the study drug. For serious adverse events, the Serious Adverse Event Form must also be completed, and the serious adverse event must be reported immediately (see Section 13.8). The investigator does not need to actively monitor subjects for adverse events once the study has ended. However, serious adverse events occurring in a subject after the treatment of that subject has ended should be reported to the sponsor if the investigator becomes aware of them.

At each contact with the subject, the investigator or designee must question the subject about adverse events by asking an open-ended question such as, "Have you had any unusual symptoms or medical problems since the last visit? If yes, please describe." All reported or observed signs and symptoms will be recorded individually, except when considered manifestations of a medical condition or disease state. A precise diagnosis will be recorded whenever possible. When such a diagnosis is made, all related signs, symptoms, and any test findings may be recorded collectively as a single diagnosis on the CRF and, if it is a serious adverse event, on the Serious Adverse Event Form.

The onset and end dates and times, action taken regarding study drug, treatment administered, and outcome for each adverse event must be recorded on the source documentation.

The relationship of each adverse event to study drug treatment and study procedures, and the severity and seriousness of each adverse event, as judged by the investigator, must be recorded as described above.

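### Inclusion 7 starts required contraception at the first dose (Day -1), although the clearing pregnancy test may be up to 20 days earlier (minor subject-safety wording)

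*Protocol*

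**What the plan says.** Inclusion 7 (Protocol 4.2) says that female subjects of childbearing potential "must be willing to use an acceptable form of birth control from the day of the first dose administration", with the obligation ending 30 days after the last dose. Only one accepted method carries a lead-in: "Medroxyprogesterone acetate-stabilized for at least 3 months". Inclusion 8 uses the same first-dose start for men.

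Two exclusions in 4.3 bear on the same question. Exclusion 1 bars pregnant or breast-feeding women and those "planning a pregnancy during the course of the study and for 30 days after last study dose". Exclusion 2 removes "Females of childbearing potential who do not agree to utilize an adequate form of contraception" and gives no start date.

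Protocol 8.1 puts the clearing test at Visit 1: "A urine pregnancy test will be conducted for all females of childbearing potential". At the same visit "the available data will be verified with the inclusion and exclusion criteria", and the subject is then randomized. Appendix I places Visit 1 at Day -21 to Day -1 and shows no later eligibility review. The next test is on Day 0 (Protocol 8.2, item 3): "Urine Pregnancy Test (for all females of childbearing potential)". By then the subject should have taken the Day -1 dose at home. SAP 7.1.1 treats that Day -1 dose as the first dose, and SAP 7.8.9 plans 17 doses in all.

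**The concern.** A negative test at Visit 1 describes the subject on that day. Its value at the first dose depends on contraception in between, and inclusion 7 sets no requirement for those days. Taken alone, it is satisfied by a woman who uses no method until Day -1.

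An unplanned conception in the interval would be found at the Day 0 test at the earliest, after at least one drop of masked study drug. The subject would then be discontinued (Protocol 9.0) and the pregnancy followed to its outcome (Protocol 13.9). What is at stake is a small, avoidable exposure of a subject. Neither the equivalence comparison nor the superiority comparison depends on it.

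**Working it through.** The plan states no figure for this interval, so there is none to reproduce. The check is day arithmetic on the visit schedule and a comparison of the relevant rules.

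**Inputs**
- Visit 1 and its urine test: Day -21 to Day -1 (Protocol 8.1, Appendix I).
- First dose: Day -1 (Protocol 11.6, SAP 7.1.1).
- Next urine test: Day 0, listed ahead of the pre-operative drop (Protocol 8.2, items 3 and 6).
- Last planned dose: Day 14, with contraception required for a further 30 days (Protocol 11.6, inclusion 7).
- Planned doses: 17, with two on Day 0 (SAP 7.8.9).

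**Interval from clearing test to required contraception**
- Longest: (-1) - (-21) = 20 days.
- Shortest: (-1) - (-1) = 0 days.
- The visit table in SAP Appendix 11.1 shows Visit 1 at Day -7 to -1, which would give (-1) - (-7) = 6 days. The protocol governs conduct, so 20 days is the relevant maximum.

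**Duration of required contraception**
- End: Day 14 + 30 = Day 44.
- As written: 44 - (-1) = 45 days.
- With a Visit 1 start at Day -21: 44 - (-21) = 65 days.
- Added: 0 to 20 days, according to when Visit 1 falls.

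**Doses taken before the Day 0 test**
- As planned: 1/17 = 5.9%. The other 16 follow the test if the checklist order is kept.
- After one cancelled surgery: SAP 7.1.1 has the subject stop and apply a new drop before the new date. If no test was done on the cancelled date and all other doses are as planned, this is (1 + 1)/(17 + 1) = 2/18 = 11.1%. The SAP does not say when the cancellation occurs. A subject who had already attended Visit 2 may have been tested, so this figure is conditional.

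**Do other rules cover the interval?**

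| Rule | What it covers | What it leaves open |
|---|---|---|
| Exclusion 1 | Pregnancy planned during the study. The one stated study period, for adverse-event recording in Protocol 13.5, runs "from signature of the informed consent form through the end of the study" | Unplanned conception |
| Exclusion 2 | Refusal to agree to contraception | The start date |
| Visit 1 eligibility check | Status and agreement on that day | The days up to Day -1 |
| Day -1 telephone call | Reminder to dose and to bring diary and drug, with adverse-event assessment | No pregnancy check |
| Day 0 test | Detection | It follows the first drop |

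No row gives a contraception start date earlier than Day -1.

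**The case against.** The strongest reply is that the rule is deliberate and the interval already largely covered. Contraception is tied to drug exposure, and the same start is used for men. By the end of Visit 1 a woman must be non-pregnant, not planning a pregnancy and willing to use contraception. What remains is an unplanned conception in someone who has already agreed to contraception. The test on Day 0 limits planned exposure before detection to one eye drop.

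The label in Appendix III limits the harm further. It does not list pregnancy as a contraindication. It reports no teratogenicity in rats or rabbits at plasma exposures 20 to 630 times human exposure, and its specific advice to avoid use concerns late pregnancy. It is also Pregnancy Category C, reports other effects in rats at maternally toxic doses, and notes the lack of adequate studies in pregnant women. Finally, the consent form is not among the pages available and may itself say when contraception begins.

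These arguments establish that the risk is very small. They do not supply the missing date: exclusion 1 concerns intention, exclusion 2 has no start, and the Day 0 test detects exposure after it has happened. It is also fair that the remedy does not improve detection. A conception just before Visit 1, or a contraceptive failure, would still be found only after the first drop.

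A reader might infer more from the pregnancy-test paragraph in Protocol 5.1. It exempts surgically sterilized women without repeating the statement in 4.2 that tubal ligation does not count, which could look like a conflict leaving some women untested. The documents do not support that. Section 4.2 settles what counts as surgically sterile and 5.1 uses the matching term. Inclusion 6 requires a negative test for women of childbearing potential as 4.2 defines them, and the checklists for Visits 1, 2 and 5 use the same category. A cross-reference is the only thing missing.

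**Conclusion.** The point holds as a minor subject-safety improvement. For 0 to 20 days after the clearing test, no dated contraception requirement applies, and the next test follows at least one dose: 1 of 17 as planned, or 2 of 18 after one cancelled surgery if no test was done on the cancelled date. The number of women concerned is not given. It is assumed to be small in a cataract population, although eligibility begins at 18 years.

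It would go too far to say that the interval is unprotected, because exclusions 1 and 2 and the Visit 1 eligibility check cover it in part. No effect on the primary endpoint, analysis populations, sample size or error rates follows.

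**What to change.** In inclusion 7, start the contraception requirement at Visit 1, the day of the clearing urine test, and keep the end at 30 days after the last dose. This also removes any question of which drop counts as the first when surgery is rescheduled. Leave inclusion 8 unchanged: the concern is a pregnancy already present in the subject at her first dose, and the requirement on her covers that.

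As an editorial matter in the same amendment, let the childbearing-potential sentence in 5.1 refer to the definition in 4.2.

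The cost is 0 to 20 more days of required contraception for the few women concerned (from 45 to at most 65 days) and an amendment approved by the sponsor and IRB under Protocol 15.7 across about 17 sites, with matching consent text if it repeats inclusion 7. No test, visit or window changes, so the edit could go into the next planned amendment.
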